9.5.3 Model checking

The assumption of normally distributed residuals will be evaluated by visual inspection of quantile-quantile plots for the primary and key secondary endpoints. If the square root transformation does not result in a good approximation to the normal distribution, no transformation will be applied if this improves the approximation to a normal distribution.

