7	Supportive secondary endpoint: DMS 1st PGPS	Supportive secondary endpoint: DMS 2nd PGPS
8	Supportive secondary endpoint: DMS 1st EGPS	Supportive secondary endpoint: DMS 2nd EGPS

Table 11Summary of MMRM response variables.

The relevant endpoints in 1st and 2nd years are set to be the response variables and treatment, visit, treatment/visit interaction as well as asthma indication (yes/no) are fixed effect and trial site as a random class effect. If less than 20% of subjects will have asthma indication positive, then the asthma indication will be removed from the model. The compound symmetry covariance matrix is considered. In case there will be issues with convergence, first-order autoregressive covariance matrix will be considered. Depending on the number and size of trial sites, pooling of trial sites may be considered, or trial sites may be replaced by regions or countries. This will be specified in the SAP. The summary of the results will contain p-value for the treatment effect, and both the absolute difference with 95% CI and the relative difference with 95% CI will be presented. If the assumptions underlying the MMRM are not fulfilled an appropriate transformation (e.g. the square root) of the response variables will be carried out. Results will be back-transformed and shown on

Clinical trial protocol Trial ID: SU-G-01 EudraCT No. 2020-000455-12 CONFIDENTIAI	Date: Version: Status: Page:	12-Nov-2021 4.0 Final 63 of 77	
CONFIDENTIAL	гауе.	03 01 7 7	

the original scale. Further details of the primary analysis, test of assumptions, and sensitivity analysis will be detailed in the SAP.

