6.5 Changes and/or deviations to protocol-planned analyses

Several changes were made to the statistical analysis described in the trial protocol. The list of changes is summarised in this section:

- PP analysis set is removed from analysis sets used in this trial. This analysis set does not align with the estimand framework; therefore, it will not be used in this trial.
- Safety and tolerability objectives and endpoints are added as supportive secondary endpoints.
- As described in the estimand framework, the most important IE is the discontinuation of IMP. The IMP discontinuation was not collected in the relevant manner in eCRF. Discontinuation of IMP is then re-classified based on reported IMP discontinuation and trial withdrawal reason (see Section 6.1.2), and these re-classified reasons are used in the estimand framework.
- In this trial, subjects were stratified based on their history of asthma in adulthood. During the trial, it was determined that it is most relevant for interpretation of the disease and treatment is ongoing asthma status at screening. Therefore, the asthma status at screening will be used in the analysis models instead of asthma strata. Twenty one subjects were stratified as asthmatics but did not have ongoing asthma at screening. Subjects with ongoing asthma are expected to be well-balanced between treatment arms.
- In the protocol, the primary and key secondary endpoint estimator contains the trial site/country as a random effect. In SAP, county and year interaction is a random effect. The change accounts for the variability of pollen load yearly in each country.
- In the protocol, the proposed MCID is 0,16. Since the protocol proposal, additional research was performed and based on published results presented new MCID for PGPS is 0,1 and EGPS 0,22 (**Blaiss et al. 2022**).
- Pollen season end date and pollen peak definition a modified to add clarity. Pollen season end date is specified that it is the last day of the last occurrence of 3 consecutive days with pollen count larger or equal to 10 grains/m³. For the peak season it is specified the 14 consecutive days period is used as a peak.

7 Sample size determination

General considerations

In this trial, primary and secondary endpoints will be tested hierarchically to control the familywise error rate at 5% level. Individual endpoint analyses will be based on treatment comparisons using a 2-sided t-distributed test on a 5% level of significance.

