The power calculations were done in two steps. This sample size wasthen evaluated using the estimand framework. The power was calculated for both the primary endpoint (TCS) and the key secondary endpoint (RQLQ). It is expected that the treatment difference in overall RQLQ during peak season is greater than the MCID of 0.10 and during entire season greater than 0.22 (Blaiss et al. 2022).

TCS power calculation

The estimated TCS mean, standard deviation and treatment differences during the peak season from three trials is presented in Table 8. The power calculation is based on a TCS treatment difference of 21% (1.64 in absolute value) and a common standard deviation of 5.5. Under these assumptions, the trial has a power of 80% with the sample size of 180 evaluable subjects. The power is 86% for the primary estimand and 80% for the secondary estimand with the assumption that 10% out of 220 subjects will discontinue the trial, with 4.5% of subjects discontinuing due to AEs and 1% due to lack of efficacy each year.

Trial	Placebo $\mu(\sigma)$	Active $\mu(\sigma)$	Difference absolute (relative)
GT-08 2006	8.44 (5.48)	5.14 (4.06)	3.3 (39%)
P05238	7.74 (6.50)	6.10 (5.09)	1.64 (21%)
P08067	5.73 (5.03)	4.56 (4.60)	1.17 (20%)
Average			2.04

Table 8: Mean and standard deviation of TCS during the peak of a season.

RQLQ power evaluation

The estimated RQLQ mean, standard deviation and treatment differences during the peak season from 3 trials raw data is presented in Table 9 below.

Table 9: Mean and standard deviation of RQLQ during the peak of a season.

Trial	Placebo $\mu(\sigma)$	Active $\mu(\sigma)$	Difference Absolute (relative)
GT-08 2005	1.82 (1.11)	1.37 (0.97)	0.45 (25%)
GT-08 2006	1.48 (1.05)	1.05 (0.91)	0.43 (29%)
P05238	1.73 (1.34)	1.41 (1.12)	0.33 (18%)
P08067	1.73 (1.34)	1.18 (1.08)	0.15 (11%)
Average	0.34		

A common standard deviation of 1.15 has been assumed in the power evaluation. An expected placebo mean is 1.60 and an expected treatment difference is 0.34. With 180 evaluable

Statistical analysis plan
Trial ID: SU-G-01
EudraCT No.: 2020-000455-12
CONFIDENTIAL

subjects per treatment arm, the power of 98% is reached for testing if RQLQ treatment difference is greater than proposed MCID of 0.1. The power is 95% for the primary and 92% secondary estimands for the sample size of 220 subjects with the same discontinuation assumptions as for TCS.

Conclusion

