The suggested sample size is 180 evaluable subjects per treatment arm. 220 subjects should be randomised in each arm, assuming a 10% discontinuation of subjects per year, where 1% discontinued due to lack of efficacy and 4.5% due to AEs. In such case, the trial has a power of at least 80% in order to detect a statistically significant difference of at least 21% with common standard deviation no larger than 5.5 for primary endpoint in observed case scenario. The trial has a power of 86% and 80% for primary endpoint for primary and secondary estimands respectively. Similarly, 95% and 92 % power for RQLQ for the primary and secondary estimand 0.1 in RQLQ for observed case.

8 Demographics and baseline characteristics

Summaries for numerical variables tables will display the descriptive statistics such as: mean, SD, median, min and max.

Summaries for categorical variables frequency tables will display counts and percentages.

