9.5.1 Transformations

Some endpoints will be square root transformed before (formal statistical) analysis. The square root transformation is generally applied, as this usually results in a good approximation to the normal distribution. In addition, a lot of subjects do not use rescue medication, so the average DMS score is often 0, and this will also be accounted for by using the square root transformation in contrast to the logarithmic transformation. The transformed endpoint is then included in the model as a response variable.

The p-value for the absolute difference will be reported as the test result and no backtransformation will be done. To enable reporting of relative difference on the original scale, transformed means will be back-transformed (see **Error! Reference source not found.**) and 95% CI will be calculated using the methods described in Figure 3. For the absolute difference,

Statistical analysis plan	Date:	27-Oct-2023		
Trial ID: SU-G-01	Version:	1.0	1	,
EudraCT No.: 2020-000455-12	Status:	Final		
CONFIDENTIAL	Page:	39 of 47		

the SE is approximated using the first-order Delta method (first-order Taylor approximation), and the 95% CI is calculated from this.

$\sqrt{()}$ -transformation

Means, differences between means and relative differences

For $\sqrt{()}$ -transformed endpoints the back-transformations (to the original scale) are :

$$\hat{\mu}_i = (\hat{\tilde{\mu}}_i)^2,$$

where $\hat{\mu}_i$ is the *i*'th treatment mean on the $\sqrt{()}$ -transformed scale. Similarly, back-transformed differences between group means are

$$\hat{\delta}_{ii'} = (\hat{\tilde{\mu}}_i)^2 - (\hat{\tilde{\mu}}_{i'})^2,$$

and relative differences are thus

$$\hat{\rho}_{ii'} = \frac{(\hat{\tilde{\mu}}_i)^2 - (\hat{\tilde{\mu}}_{i'})^2}{(\hat{\tilde{\mu}}_{i'})^2}.$$

The estimates $\hat{\mu}_i$, $\hat{\mu}_{i'}$ (that is, on the $\sqrt{()}$ -transformed scale) are obtained from proc mixed's lsmeans statement.

Standard errors

The variances of the back-transformed parameters follow from the δ -method

$$\operatorname{SE}(\hat{\mu}_i) = 2\hat{\tilde{\mu}}_i \times \operatorname{SE}(\hat{\tilde{\mu}}_i).$$

with the variance (SE) of $\hat{\delta}_{ii'}$ following alike :

$$\operatorname{SE}(\hat{\delta}_{ii'}) = 2\sqrt{\hat{\mu}_i^2}\operatorname{SE}^2(\hat{\mu}_i) + \hat{\mu}_{i'}^2\operatorname{SE}^2(\hat{\mu}_{i'}) - 2\hat{\mu}_i\hat{\mu}_{i'}\widehat{\operatorname{cov}}(\hat{\mu}_i, \hat{\mu}_{i'}).$$

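### The scale of the confirmatory tests rests on a visual residual check with no criterion, timing or blinding condition, and the SAP reverses the protocol's default without listing the change

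*SAP*

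**What the plan says.** - **Protocol 15.11.1** analyses the untransformed response and transforms only on failure: "If the assumptions underlying the MMRM are not fulfilled an appropriate transformation (e.g. the square root) of the response variables will be carried out". It leaves the details of the assumption checks to the SAP.
- **SAP 9.5.1** starts from the other end: "Some endpoints will be square root transformed before (formal statistical) analysis". The endpoints are not listed, although the section describes the square root as the usual choice. The p-value on the analysed scale is the test result.
- **SAP 9.5.3** judges residual normality for the primary and key secondary endpoints by eye from quantile-quantile plots. If the square root does not give a good approximation, "no transformation will be applied if this improves the approximation to a normal distribution". There is no threshold, assessor, timing or blinding condition. Nor does it say which of the 1,000 imputed data sets is inspected.
- **SAP 9.5.2** specifies the model whose residuals would be plotted. It contains treatment by year and separate R-matrices for the two arms.
- **Protocol 6.2 and 14.5** release the treatment codes only once the database is locked.
- **SAP 6.5**, where SAP section 3 says changes to the protocol analyses are recorded, does not mention the reversed order of scales.

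**The concern.** The hierarchy in SAP 4.1 presumes one pre-specified test per hypothesis. Here the scale of the test can change on a judgement that two competent statisticians could make differently. The residuals come from a model that needs the treatment codes, so the fitted results would be available to whoever makes that judgement. TCS in the 2nd PGPS is the first step of the hierarchy, so the choice of scale can also decide whether the three key secondary endpoints are formally tested. A reader who compares the two documents finds opposite defaults and no explanation.

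**Working it through.** **Timing, by inference.** The arm-specific residuals of SAP 9.5.2 cannot be formed without treatment codes. The codes arrive at lock, when the data are unblinded. No blinded or pooled check is described. The check as written can therefore only follow unblinding, although no sentence says so.

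**The plan's own power figure.** SAP section 7 plans to test "using a 2-sided t-distributed test on a 5% level of significance", with "The power calculation is based on a TCS treatment difference of 21% (1.64 in absolute value) and a common standard deviation of 5.5" and 180 evaluable subjects per arm.
- Standard error: 5.5 × √(2/180) = 0.580. Ratio: 1.64/0.580 = 2.83.
- Power: Φ(2.83 − 1.96) = Φ(0.87) ≈ 80.8%. The exact noncentral t gives 80.5%.

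The stated 80% reproduces, but as power on the untransformed scale. The documents give no power for the square-root scale, which is the SAP's default.

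**How far the two scales can differ.** The documents do not give the shape of the TCS distribution, so two shapes are assumed: gamma (skewed), and normal clipped to 0–38. Each scenario has 40,000 simulated trials of 180 per arm, with single-season Welch t-tests on raw and square-root TCS. The mechanical rule takes the scale whose residuals correlate better with normal quantiles. MMRM and imputation were not simulated, and neither was RQLQ. The Monte Carlo standard error at 5% is √(0.05 × 0.95/40,000) ≈ 0.11 points.

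Same distribution in both arms, SD 5.5 (% of trials significant):

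| Shape, mean | Raw | Square root | Mechanical rule | Smaller p always taken |
|---|---|---|---|---|
| Gamma, 7 | 5.0 | 5.1 | 5.1 | 6.1 |
| Gamma, 7.74 | 5.1 | 5.0 | 5.0 | 6.1 |
| Clipped normal, 7 | 5.2 | 5.1 | 5.3 | 6.6 |
| Clipped normal, 7.74 | 5.0 | 5.0 | 5.1 | 6.4 |

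Means 7.74 (placebo) and 6.10 (active), from P05238 in SAP Table 8; difference 7.74 − 6.10 = 1.64:

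| Shape, SDs (placebo, active) | Raw power | Square-root power | Scales disagree |
|---|---|---|---|
| Gamma, 5.5 and 5.5 | 80% | 94% | 14% |
| Gamma, 6.50 and 5.09 | 76% | 73% | 7% |
| Clipped normal, 5.5 and 5.5 | 79% | 78% | 7% |
| Clipped normal, 6.50 and 5.09 | 88% | 59% | 28% |

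For the clipped shape, the means and SDs are those before clipping. Using E[max(0, X)] = mΦ(m/s) + sφ(m/s), the realised differences are about 1.47 (equal SDs) and 1.72 (P05238 SDs).

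Under gamma the mechanical rule chose the square root in effectively every trial. Under the clipped normal it chose raw in at least 97% of the trials tabulated. The scale that results therefore depends on a TCS shape that the documents do not describe.

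**The case against.** The strongest reply is that SAP 9.5.3 is not an open choice. It has a default and a single fallback, which needs two conditions: the square root fails and the raw scale improves matters. Both concern normality, not significance. A residual plot does not display the treatment contrast. The protocol foresaw that the SAP would settle these details, and the SAP states that it was approved before lock and unblinding. All of this stands.

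It rules out two stronger readings that a reader might infer:
- *The 5% error rate is lost.* The documents do not support this. Followed as written, the rule stays near 5% in the scenarios with equal distributions. The 6.1 to 6.6% figure requires always taking the smaller p-value, which the SAP does not allow.
- *The plan states that the scale is chosen after unblinding, with results in view.* The timing is a sound inference from the model and the release of codes, but SAP 9.5.3 gives none.

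Disagreement between scales also does not measure harm from the rule. In the gamma scenario with equal SDs, almost all of it favours the square root, so falling back could only lose significance. With P05238 SDs, raw-only significance occurs in about 5% of gamma trials, so discretion could work the other way.

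Because SAP 9.5.3 covers the primary and key secondary endpoints, the fair reading is that the square root is their default, despite the loose wording of 9.5.1. The code of SAP Appendix A is not in the text available here and may name the scale.

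What the reply does not answer is the missing criterion, timing and blinding condition, and the unlisted reversal of the protocol's order.

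**Conclusion.** The point holds as a gap in pre-specification. A visual judgement without a criterion, by inference made after unblinding, selects between two tests that disagree on significance in roughly 7 to 28% of simulated trials built on the planned difference. That range rests on assumed TCS shapes, on SDs of 5.5 or those of P05238, on 180 per arm, and on simple two-sample tests in place of the MMRM with imputation. Type I error under mechanical use is about 5.0 to 5.3%, and 6.1 to 6.6% is the ceiling under abuse.

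The error figures assume identical distributions in the two arms. With equal gamma means of 7 but SDs of 6.50 and 5.09, the square-root test rejects in 13.9% of trials against 4.9% for raw, because it tests a different quantity. That mismatch with the difference-in-means estimand of SAP 3.1.1.2 is a separate issue, and fixing the scale does not by itself resolve it.

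**What to change.** 1. In SAP 9.5.1, name one scale for TCS and one for RQLQ, and likewise for the other endpoints.
2. Fix the choice before unblinding, using residuals from pooled blinded data and a model without treatment. The SAP gives the last subject's last visit as 22-Sep-2023 and is itself dated 27-Oct-2023, before lock by its own statement, so blinded diary data could have served for this.
3. Delete the switching sentence in SAP 9.5.3. Keep the plots as description only.
4. List the departure from protocol 15.11.1 in SAP 6.5, with the reason.
5. Report the other scale as a sensitivity analysis that cannot replace the confirmatory result.

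If unblinding has already taken place, report both scales and state when, by whom and on what evidence the scale was chosen.

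The cost is a few lines of SAP text and one blinded check. The downside is that the chosen scale is kept even if the unblinded residuals look slightly worse.

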9.5.7 Analysis of quality-of-life questioners

The overall RQLQ score during V3 (1st off-season) at randomisation and at the end of trial will be analysed via descriptive statistics. Descriptive statistics by treatment include number of subjects, mean, standard deviation, median, minimum, and maximum.

9.5.8 Convergence issues

If any models defined above do not converge, several attempts will be made to reach convergence:

- The first step will be set the same R-matrice among the two treatment arms.
- The second step will be to change the unstructured covariance matrix to the compound symmetry matrix.
- The third step we will be to remove ongoing asthma status from the model.
- The fourth step we will be to be to pool countries into regions.
- The fifth step will be to remove the random effect of region and year interaction from the model.

10 References

ICH 2020: ICH E9 (R1) addendum on estimands and sensitivity analysis in clinical trials to the guideline on statistical principles for clinical trials EMA/CHMP/ICH/436221/2017.

Chang et al. 2019: Chang, E. M., Gillespie, E. F., & Shaverdian, N. (2019). Truthfulness in patient-reported outcomes: factors affecting patients' responses and impact on data quality. Patient related outcome measures, 10, 171–186. https://doi.org/10.2147/PROM.S178344.

Juniper et al. 1998: Juniper, E. F., Howland, W. C., Robertsa, N. B., Thompson, A. K., & King, D. R. (1998). Measuring quality of life in children with rhinoconjunctivitis. Journal of allergy and clinical immunology, 101(2), 163-170.

Rubin 1987: Rubin, D.B. (1987) Multiple Imputation for Nonresponse in Surveys. John Wiley & Sons Inc., New York. http://dx.doi.org/10.1002/9780470316696.

Blaiss et al. 2022: Blaiss, M. S., Gronskyte Juhl, R., Siew, L. Q., Hammerby, E., & Devillier, P. (2022). Determining the minimal important differences in the RQLQ score with grass and tree allergy immunotherapy versus placebo in adults with moderate-to-severe allergy. Allergy, 77(6), 1843-1851.

 Date:
 27-Oct-2023

 Version:
 1.0

 Status:
 Final

 Page:
 43 of 47

Appendix A: SAS codes

Primary efficacy analysis

Appendix B: pollen seasons start and stop dates

Pollen station	Sites	Year	Season	Start date	Stop date	Comment
CZBRNO	207	2022	EGPS	19MAY2022	04JUL2022	
			PGPS	31MAY2022	13JUN2022	
		2023	EGPS	25MAY2023	20JUL2023	
			PGPS	20JUN2023	03JUL2023	
CZCEBU	203, 212	2022	EGPS	19MAY2022	18JUL2022	
			PGPS	02JUN2022	15JUN2022	
		2023	EGPS	22MAY2023	25JUL2023	Missing data
			PGPS	29JUN2023	12JUL2023	CZJIHL.
CZJIHL	205	2022	EGPS	18MAY2022	23JUL2022	
			PGPS	07JUN2022	20JUN2022	
		2023	EGPS	22MAY2023	25JUL2023	
			PGPS	29JUN2023	12JUL2023	
CZLIBE	209, 211, 213	2022	EGPS	24MAY2022	15JUL2022	
			PGPS	06JUN2022	19JUN2022	
		2023	EGPS	28MAY2023	16JUL2023	
			PGPS	31MAY2023	13JUN2023	
CZUORL	202, 210	2022	EGPS	31MAY2022	19JUN2022	
			PGPS	03JUN2022	16JUN2022	
		2023	EGPS	22MAY2023	25JUL2023	Missing data
			PGPS	29JUN2023	12JUL2023	CZJIHL.
EETALL	302	2022	EGPS	15JUN2022	12AUG2022	
			PGPS	17JUN2022	30JUN2022	
		2023	EGPS	15JUN2023	19JUL2023	Dates were adjusted after visual inspection.
			PGPS	15JUN2023	28JUN2023	

FRAMIE	676	2022	EGPS	09MAY2022	20JUL2022	
			PGPS	06JUN2022	19JUN2022	
		2023	EGPS	18MAY2023	16JUL2023	
			PGPS	03JUN2023	16JUN2023	
FRBRUL	635	2022	EGPS	11APR2022	29JUL2022	
			PGPS	14MAY2022	27MAY2022	
		2023	EGPS	02MAY2023	30JUL2023	
			PGPS	24MAY2023	06JUN2023	
FRCHOL	601	2022	EGPS	02MAY2022	14JUL2022	
			PGPS	14MAY2022	27MAY2022	
		2023	EGPS	05APR2023	12JUL2023	
			PGPS	26MAY2023	08JUN2023	
FRNARB	636	2022	EGPS	13APR2022	18JUL2022	
			PGPS	17MAY2022	30MAY2022	
		2023	EGPS	28APR2023	12JUL2023	
			PGPS	16MAY2023	29MAY2023	
FRORLE	632	2022	EGPS	20MAY2022	16JUL2022	
			PGPS	21MAY2022	03JUN2022	
		2023	EGPS	03MAY2023	23JUL2023	
			PGPS	22MAY2023	04JUN2023	
FRSTRA	670	2022	EGPS	07MAY2022	07JUL2022	
			PGPS	20MAY2022	02JUN2022	
		2023	EGPS	04MAY2023	20JUL2023	
			PGPS	23MAY2023	05JUN2023	
FRTOUL	631	2022	EGPS	04MAY2022	20JUN2022	
			PGPS	18MAY2022	31MAY2022	
		2023	EGPS	02MAY2023	24JUL2023	
			PGPS	23MAY2023	05JUN2023	
FRTOUN	633	2022	EGPS	29APR2022	18JUN2022	

			PGPS	18MAY2022	31MAY2022	
		2023	EGPS	10MAY2023	03JUL2023	
			PGPS	15JUN2023	28JUN2023	
LTVILN	501, 502, 503, 504, 506, 507, 508	2022	EGPS	10JUN2022	05JUL2022	
			PGPS	18JUN2022	01JUL2022	
		2023	EGPS	09JUN2023	01JUL2023	Dates were adjusted after visual inspection.
			PGPS	09JUN2023	22JUN2023	
LVRIGA	401, 402, 403, 404, 405, 406	2022	EGPS	05JUN2022	23JUL2022	
			PGPS	23JUN2022	06JUL2022	
		2023	EGPS	10JUN2023	21JUL2023	Dates were adjusted after visual inspection.
			PGPS	10JUN2023	23JUN2023	
PLBYDG	105, 106, 109,	2022	EGPS	13MAY2022	11AUG2022	
			PGPS	24JUN2022	07JUL2022	
		2023	EGPS	21MAY2023	26AUG2023	
			PGPS	25JUN2023	08JUL2023	
PLCRAC	102, 108, 110, 112, 113, 114	2022	EGPS	29MAY2022	11JUL2022	
			PGPS	24JUN2022	07JUL2022	
		2023	EGPS	26MAY2023	25JUL2023	
			PGPS	29JUN2023	12JUL2023	
PLLUBL	103	2022	EGPS	31MAY2022	10JUL2022	
			PGPS	22JUN2022	05JUL2022	
		2023	EGPS	25MAY2023	15AUG2023	
			PGPS	26JUN2023	09JUL2023	
PLPTRY	104, 115	2022	EGPS	10MAY2022	11AUG2022	
			PGPS	31MAY2022	13JUN2022	

Date:	27-Oct-2023
Version:	1.0
Status:	Final
Page:	47 of 47

		2023	EGPS	23MAY2023	14AUG2023	
			PGPS	25JUN2023	08JUL2023	
PLWROC	101, 107, 111	2022	EGPS	13MAY2022	20JUL2022	
			PGPS	30MAY2022	12JUN2022	
		2023	EGPS	23MAY2023	21JUL2023	
			PGPS	29MAY2023	11JUN2023	

Signature Page for VV-CLIN-004975 v1.0

Signature Page for VV-CLIN-004975 v1.0
